Modified Vascularized Interpositional Periosteal Connective Tissue Graft Versus Xenogeneic Collagen Matrix For soft tissue Augmentation Around Implant in Esthetic Zone (A Comparative Study)

Proposal

Presented By

[name]

25/12/ 2024

Statistical Analysis:

Statistical analysis was performed with IBM® SPSS® (ver. 26. SPSS Inc., IBM Corporation, Armonk, NY, USA). Data explored for normality using Shapiro-Wilk test. Quantitative data were presented by mean and standard deviation. Independent t test was used to compare means between two groups. Paired t test was used to compare between two means before and after treatment within each group. A repeated measure ANOVA is used to compare means in each group across multiple times to see changes to an intervention. A statistically significant level was considered when p value < 0.05.

3. Results:

Twenty patients were recruited in the study, including 12 females and 8 males aged between 20 to 40 years; there were no failed implants or withdrawal of any patients during the follow-up period. Every one of the participants had their planned treatment, and all the implants placed osseointegrated successfully. Data are expressed as mean \pm standard deviation.

3.1 Clinical Parameters:

3.1.1 keratinized tissue thickness: KTT increased from baseline to 3, 6 months in both of groups but more improvement seen in mVIP-CT group than in XCM group at 3 and 6month. No significant differences between the study groups at baseline, but at 3 and 6 month the differences were statistically significant

3.1.2 keratinized tissue width: KTW increased from baseline to 3 ,6 months in both groups but was slightly higher in mVIP-CT group than in XCM group at 6 months with nonsignificant differences between them at baseline and follow up

3.1.3 pink esthetic score: The aesthetic outcome was measured by Pink Esthetic Score (PES), the comparison between both groups revealed a non-significantly higher results in mVIP-CT group than in XCM group

3.2. Radiographic Parameters:

3.2.1 buccal cortex thickness: increased from baseline to 6 month in both of mVIP-CT group and XCM group with no significant differences between the study groups at baseline and follow up period.

KTT	mVIP-CTG group		P value — Baseline	P value Baselin	P value 3	
	Baseline	3 months	6 months	VS	e vs 6 months	months vs 6 months
Mean±SD	1.5±0.53	1.9±0.41	2.8±0.56	0.9	0.001*	0.01*

 Table (1): Keratinized tissue thickness (KTT) level at different points of time in mVIP-CTG group

 Table (2): Keratinized tissue thickness (KTT) level at different points of time in XCM group

KTT	8 1				P value 3 months	
	Baseline	3 months	6 months	vs 3 months	vs 6 months	vs 6 months
Mean±SD	1.4 ± 0.67	1.5±0.40	2.0±0.55	0.1	0.2	0.5

KTT	Groups	P value	
	mVIP-CTG (n=10)	XCM (n=10)	
	Mean±SD	Mean±SD	
At baseline	1.5±0.53	$1.4{\pm}0.67$	0.7
3 months	1.9±0.41	1.5±0.40	0.04
6 months	2.8±0.56	2.0±0.55	0.004

Table (4): Keratinized tissue width (KTW) level at different points of time in mVIP-CTG group

KTW	mV	mVIP-CTG group		P value Baseline	P value Baseline	P value 3
	Baselin e	3 months	6 months	vs 3 months	vs 6 months	months vs 6 months
Mean±SD	1.4±0.52	1.5±0.53	2.0±0.84	0.9	0.07	0.1

 Table (5): Keratinized tissue width (KTW) level at different points of time in XCM

 group

KTW		XCM group		P value Baseline		P value 3 months
	Baseline	3 months	6 months	vs 3 months	vs 6	vs 6 months
					months	
Mean±SD	1.6±0.52	1.7±0.52	1.9±0.68	0.6	0.2	0.4

 Table (6):
 Keratinized tissue width (KTW) level between groups

KTW	Groups	P value	
	mVIP-CTG (n= 10)	XCM (n=10)	
	Mean±SD	Mean±SD	
At baseline	1.4±0.52	1.6±0.52	0.3
3 months	1.5±0.53	1.7±0.52	0.4
6 months	2.0±0.84	1.9±0.68	0.7

 Table (7): Buccal cortex thickness level at baseline and after 6 months in mVIP-CTG group

Buccal cortex thickness	mVIP-CTG group		Mean P value differenc	
	Baseline	6 months	e	
Mean±SD	0.744±0.33	1.207±0.16	-0.463	0.01

Table (8): Buccal cortex thickness level at baseline and after 6 months in XCM group					
Buccal cortex		XCM group	Mean	P value	
thickness			_ differenc		
	Baseline	6 months	e		

			· ·		
Mean±SD	$0.92{\pm}0.32$	0.97±0.31	-0.054	0.6	

Buccal cortex thickness	Groups	P value	
	mVIP-CTG (n= 10) Mean±SD	XCM (n=10) Mean±SD	
At baseline	0.744±0.33	0.92±0.32	0.2
6 months	1.207±0.16	0.97±0.31	0.06

 Table (9): Buccal cortex thickness level between groups

Table (10): Pink esthetic score (PES) between groups

	Group	s	P value
	mVIP-CTG (n= 10) Mean±SD	XCM (n=10) Mean±SD	
Pink esthetic score (PES)	6.8±0.57	6.3±0.53	0.06

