All patients will undergo an immediate implant placement and the complete treatment plan will be explained to all patients including detailed steps, risks, and expected results. Verbal and written informed consent will obtained from all patients before the commencement of the study. All experiments will be examined and approved by the appropriate ethics committee and have therefore been performed in accordance with the ethical standards laid down in the 1964 Declaration of Helsinki and the research ethics committee of the Faculty of Dentistry, Minia University.

Pre surgical phase

- All selected patients will be screened by comprehensive periodontal examination and full periodontal charts will be obtained. A preoperative cone beam computed tomography (CBCT) will be performed for each patient who met the inclusion criteria prior to the surgery to determine bone height and width and decide the implant length and diameter to be placed and to evaluate the underlying bone condition.
- Trans-gingival probing will be done at the mesial line angle 2, 4 and 6 mm apical to the gingival margin. At the same apico-coronal direction three points will be recorded at the mid-buccal and at the distal line angle (Rotenberg and Tatakis 2014)
- 3. The width of keratinized gingiva will be measured using UNC-15 probe and recorded as the distance from the mucogingival junction to the gingival margin.

Randomization

The study will use simple randomization to allocate patients into 2 groups, each group will be included 10 patients.

Then, random allocation will be performed using computer-generated random numbers to determine which group they will be assigned.

• Group 1: Immediate dental implant +Xenogenic bone graft +mVIP-CT graft technique

• Group 2: Immediate dental implant + Xenogenic bone graft+ Xenogenic collagen matrix membrane

Surgical Phase

In group 1" the mVIP-CT group "

- 1. After obtaining adequate local anesthesia (2% lidocaine HCL 1:100000 epinephrine), atraumatic extraction using periotome will done followed by immediate implant placement.
- 2. After ensuring the correct three-dimensional placement of the implant, the jumping distance between the implant and socket will grafted with xenogeic bone graft.
- 3. Soft tissue augmentation will be planned over the implant site. Modified VIP-CT graft will be harvested with modified single incision technique from the palate and the advancement will done through palatal tunneling procedure.

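### The only between-arm analysis is an unadjusted t test at each visit: baselines are tested for balance but never used to adjust, and the claim of more KTT improvement has no contrast that uses baseline

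*SAP*

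**What the plan says.** The SAP section Statistical Analysis lists three procedures. Between arms: "Independent t test was used to compare means between two groups". The other two stay inside an arm: "Paired t test was used to compare between two means before and after treatment within each group", and "A repeated measure ANOVA is used to compare means in each group across multiple times to see changes to an intervention". No covariate, between-arm test of change, or group-by-time term is named, and none appears in the tables. The Protocol's own Statistical analysis section is one general sentence that names no method.

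On allocation, the Protocol (Randomization) states: "The study will use simple randomization to allocate patients into 2 groups", with 10 patients in each.

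Baseline values do reach the between-arm tables for KTT, KTW and buccal cortex, but only as balance tests, with p=0.7, 0.3 and 0.2. SAP section 3.1.1 reports: "No significant differences between the study groups at baseline, but at 3 and 6 month the differences were statistically significant". The same section claims "more improvement seen in mVIP-CT group than in XCM group at 3 and 6month". For buccal cortex, section 3.2.1 reports "no significant differences between the study groups at baseline and follow up period", and the corresponding table is headed "Buccal cortex thickness level between groups". The pink esthetic score (PES) has one between-arm comparison and no tabulated baseline.

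**The concern.** With 20 patients and simple randomisation, sizeable chance differences at baseline are to be expected, and some are visible. A t test on follow-up means carries them into the estimated treatment difference. A non-significant balance test at this sample size does not show that the arms were alike, and it adjusts nothing.

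The KTT claim is also worded as improvement, which means change from where each arm started. The between-arm evidence behind it is a set of separate comparisons of visit means. The analyses that use baseline are separate within-arm tests, and these do not compare the arms. The reader therefore has no estimate of how much more KTT improved in one arm than in the other, and no interval for it.

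**Working it through.** **Inputs.** Means and SDs from the SAP tables, n=10 per arm, differences as mVIP-CT minus XCM. The correlation r between baseline and follow-up is not given. I assume 0.3, 0.5 and 0.7, equal in both arms.

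**1. Reproduce the stated tests.** Pooled SD = √((s₁²+s₂²)/2), SE = SD×√(2/10), 18 df.
- KTT 3 months: SD 0.405, SE 0.181, t = 0.40/0.181 = 2.21, p=0.040 (stated 0.04).
- KTT 6 months: SD 0.555, SE 0.248, t = 0.80/0.248 = 3.22, p=0.005 (stated 0.004, close enough given rounded inputs).
- KTT baseline: p=0.72 (stated 0.7).

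The KTT figures are those of a t test with no baseline term.

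**2. Baseline imbalance in pooled SDs.** KTT 0.1/0.604 = 0.17. KTW 0.2/0.52 = 0.38. Buccal cortex 0.176/0.325 = 0.54.

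**3. ANCOVA from summary statistics.** With x the baseline and y the follow-up, pooled within arm: b = Sxy/Sxx; adjusted difference = (y₁−y₂) − b(x₁−x₂); SE² = (residual SS/17)×(2/10 + (x₁−x₂)²/Sxx); 17 df.

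Example, KTT at 6 months, r=0.5:
- Sxx = 9(0.53²+0.67²) = 6.568
- Syy = 9(0.56²+0.55²) = 5.545
- Sxy = 9×0.5×(0.53×0.56+0.67×0.55) = 2.994
- b = 0.456; adjusted difference = 0.80 − 0.456×0.1 = 0.754 mm
- residual SS = 5.545 − 2.994²/6.568 = 4.180; SE = √(0.2459×0.2015) = 0.223
- t = 3.39, p=0.0035, 95% CI 0.28 to 1.22 mm

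| Outcome | Raw difference (mm) | Adjusted, r=0.3/0.5/0.7 (mm) | p |
|---|---|---|---|
| KTT 3 months | 0.40 | 0.38/0.37/0.35 | 0.048/0.037/0.018 |
| KTT 6 months | 0.80 | 0.77/0.75/0.74 | 0.006/0.004/0.001 |
| KTW 3 months | −0.20 | −0.14/−0.10/−0.06 | 0.56/0.65/0.74 |
| KTW 6 months | 0.10 | 0.19/0.25/0.30 | 0.59/0.44/0.25 |

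A plain comparison of KTT change scores (variance s₀²+s₁²−2r·s₀·s₁ per arm, 18 df) gives 0.7 mm at 6 months (p=0.035/0.015/0.003) and 0.3 mm at 3 months (p=0.29/0.23/0.14).

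**4. Rounding.** Moving each printed KTT or KTW mean by ±0.05 mm:
- KTT 3 months, ANCOVA p: 0.012–0.17, 0.007–0.17 and 0.002–0.15 at the three values of r. The raw test is similarly sensitive, 0.013–0.115.
- KTT 6 months, ANCOVA p: at or below 0.018 throughout.
- KTW 6 months, ANCOVA p: 0.07–0.90.

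**5. Precision.** SE ratio to raw = √((18/17)(1−r²)(1+5(x₁−x₂)²/Sxx)), with r pooled within arm. At r=0 this is √(1.0588×1.0076) = 1.03 for KTT, √(1.0588×1.0411) = 1.05 for KTW and √(1.0588×1.0814) = 1.07 for buccal cortex. At r=0.5 it is about 0.90 for KTT and 0.91 for KTW. At r=0.3 there is almost no gain (0.99 and 1.00).

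**6. Buccal cortex at 6 months.**
- Raw: 1.207−0.97 = 0.237 mm, SE 0.110, 95% CI 0.237 ± 2.101×0.110 = 0.01 to 0.47. Pooled p=0.046, Welch p=0.050, against the stated 0.06. Within rounding of the inputs the pooled p reaches at most 0.054 and the Welch p 0.059.
- Inferring r from the paired p-values (SD of change = d√10/t, 9 df): mVIP-CT 0.463×3.162/3.250 = 0.451, r = −0.65; XCM 0.054×3.162/0.543 = 0.314, r = +0.50.
- Slopes: −0.65×0.16/0.33 = −0.31 and 0.50×0.31/0.32 = +0.49. Their difference is 0.80, SE 0.32, t = 2.50 on 16 df, p about 0.02.
- A common-slope ANCOVA on these inputs gives 0.25 mm (95% CI 0.00 to 0.50), p=0.048, SE 0.117. Taking the XCM mean as 0.92+0.054 = 0.974 gives p=0.052. Assuming instead an equal r in both arms gives p=0.061 at r=0 and 0.010 at r=0.5.
- The inferred r is weak. Rounding of p=0.01 alone allows −0.22 to −0.98. Some within-arm p-values in this SAP also do not fit the printed SDs: for KTT in the mVIP-CT arm, baseline to 3 months, even r=−1 gives t = 0.4×3.162/(0.53+0.41) = 1.35, p=0.21, where 0.9 is stated.

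**The case against.** The strongest defence is that nothing reported is shown to be wrong. The t test is valid under randomisation. The KTT imbalance is small, and at these values of r adjustment moves the difference by only 0.02 to 0.06 mm, less than the 0.1 mm to which the means are printed. KTW stays non-significant. Results are already in hand, so any ANCOVA is chosen after the outcome is known, with 20 patients. The KTT wording could be corrected without any new model. All of this stands. It limits the size of the point but does not supply a contrast that uses baseline.

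Three stronger readings are tempting and not supported:
- *The between-arm tests are invalid or inflate the type I error.* They are not shown to be; the loss is uncorrected chance imbalance and possibly precision.
- *Adjustment overturns the 3-month KTT result.* The change-score p-values might suggest so, but ANCOVA is the more efficient contrast and stays below 0.05 at the printed means. The documents show only that the result is fragile, and the raw test is fragile too.
- *Adjustment turns the buccal cortex null into a positive finding.* The result is borderline before any adjustment, on the printed means and SDs. The common-slope estimate moves it by only 0.013 mm, with a larger SE, and the inferred slopes conflict.

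**Conclusion.** The concern holds in this limited form: the SAP has no between-arm analysis that uses baseline, although the baselines exist and no patient withdrew. Adding one is advisable rather than essential.

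For r between 0.3 and 0.7, the 6-month KTT difference is robust. The 3-month KTT difference is borderline and sensitive to rounding. The 6-month KTW estimate moves most in relative terms but remains non-significant (in the same calculation p falls below 0.05 only at r near 0.9). The documents do not determine the adjusted buccal cortex result. What can be said is that the raw result is borderline, and that its stated p of 0.06 sits slightly above what the printed means and SDs give.

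These figures assume the printed means and SDs, n=10 per arm, two-sided tests and, for KTT and KTW, an equal r in both arms.

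**What to change.** Fix one model form before the re-run: follow-up value on arm plus the patient's own baseline, for KTT and KTW at 3 and 6 months and for buccal cortex at 6 months. Report the adjusted differences with 95% CIs beside the existing t tests, whatever their direction, and label them post hoc. Base the KTT improvement statement on the adjusted contrast, or reword it to say that mean KTT was higher at 3 and 6 months.

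For buccal cortex, check the arm-by-baseline slopes on patient-level data first. If they clearly differ, say that a common-slope estimate is unreliable. In either case report the raw difference with its CI and check the stated p. PES has no tabulated baseline, so its unadjusted comparison stays.

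The cost is one degree of freedom (17 instead of 18) and a re-run on the patient-level data. If r is near 0, the SE grows by about 3% (KTT), 5% (KTW) or 7% (buccal cortex). The post hoc label does not fully remove the limitation of choosing the model after seeing the results.

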Previous studies have investigated the clinical efficacy of XCM for augmenting keratinized mucosa and reported promising results (Schmitt, Moest et al. 2016).

So, our research aiming to compare between modified VIP-CT graft and xenogenic collagen matrix membrane for soft tissue augmentation around dental implant in esthetic zone.

Aim of the study

-The primary aim of this study is to evaluate the efficacy of mVIP-CT graft technique for soft tissue augmentation around dental implant in esthetic zone.

-The secondary aim is to compare between mVIP-CT graft and xenogenic collagen matrix membrane for soft tissue augmentation around dental implant in esthetic zone.

Patients and methods

Patient selection

This study will be conducted on 20 patients with missing maxillary teeth in esthetic zone seeking its replacement. After approval from the ethical committee, patients will select from the outpatient clinic, Department of Oral medicine, Diagnosis and Periodontology, Faculty of Dentistry, Minia University.

Inclusion criteria

- 1. Selected patients of both sexes are 20-40 years old.
- Patients are systemically healthy based on questionnaire dental modification of Cornell index.
- 3. Good oral health
- 4. The recipient site of the implant is free from any pathological conditions.
- 5. Necessity for soft tissue volume augmentation at the buccal implant site (thin gingival biotype with a narrower zone of keratinized tissue & decrease in papilla height)
- 6. Adequate interocclusal space to accommodate the available restorative components.
- 7. Adequate native/apical bone to achieve primary implant stability.

Exclusion criteria:

- 1. Pregnant female
- 2. Parafunctional habits such as bruxism and clenching Patients suffering from periodontitis.
- 3. Untreated periodontitis and poor oral hygiene
- 4. Patients underwent any prior periodontal surgery in the relevant region for at least 6 months prior to this study
- 5. Smokers.

Ethical regulation

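### Two within-group KTT p-values (Table 1 baseline to 3 months, 0.9; Table 2 3 to 6 months, 0.5) cannot come from the paired t-test the SAP names, and no follow-up test or adjustment is stated that would explain them

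*SAP*

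**What the plan says.** The SAP's Statistical Analysis section names two within-group methods. For two time points: "Paired t test was used to compare between two means before and after treatment within each group". For more than two: "A repeated measure ANOVA is used to compare means in each group across multiple times to see changes to an intervention". It names no pairwise follow-up to the ANOVA, no multiplicity adjustment and no rank-based alternative.

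Tables 1 and 2 nevertheless give three pairwise p-values per arm for KTT, in the order baseline to 3 months, baseline to 6 months, 3 to 6 months.

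- Table 1 (mVIP-CT): baseline 1.5±0.53, then "1.9±0.41 2.8±0.56 0.9", where the last figure is the p-value for baseline to 3 months. The other two are 0.001 and 0.01.
- Table 2 (XCM): baseline 1.4±0.67, then "1.5±0.40 2.0±0.55 0.1 0.2 0.5".

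The Protocol, under Aim of the study, says: "The primary aim of this study is to evaluate the efficacy of mVIP-CT graft technique". Table 1 is the within-group KTT evidence on that aim.

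**The concern.** A rise of 0.4 mm with SDs of about 0.5 in 10 patients should not give p = 0.9. Table 4 prints the same 0.9 for keratinized tissue width, where the change is only 0.1 mm: "1.5±0.53 2.0±0.84 0.9 0.07 0.1". In Table 2 the smallest change (0.1 mm) carries the smallest p-value (0.1), and a 0.5 mm change carries the largest (0.5).

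As printed, a reader would conclude that mVIP-CT shows no KTT gain by 3 months and that XCM shows none between any two visits. If those p-values are wrong, the within-group evidence on the primary aim is misreported, and the within-group difference between the two grafts may look sharper than it is.

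**Working it through.** **Inputs.** Means, SDs and printed p-values are from SAP Tables 1 and 2. n = 10 per arm is from Table 3, and section 3 (Results) reports no withdrawals, so there are 10 pairs at each visit. Tests are taken as two-sided. The within-patient correlation r is not reported, so the whole range −1 to +1 is examined.

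**Control: the plan's own figures.** Independent t-tests on the same means and SDs (df 18) give 0.716, 0.040 and 0.0047, against 0.7, 0.04 and 0.004 in Table 3. The means, SDs and n therefore fit together, and the two-sided reading is right for that table.

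**Paired t-test.** t = d√10 / SD_diff, with SD_diff² = s₁² + s₂² − 2·r·s₁·s₂ and df = 9. SD_diff is largest at r = −1, where it equals s₁ + s₂; that gives the largest possible p.

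- Table 1, baseline to 3 months: t ≥ 0.4 × 3.162 / 0.94 = 1.35, so p ≤ 0.211. A p of 0.9 would need SD_diff = 9.8 mm against a ceiling of 0.94.
- Table 2, 3 to 6 months: t ≥ 0.5 × 3.162 / 0.95 = 1.66, so p ≤ 0.130. A p of 0.5 would need SD_diff = 2.25 mm against a ceiling of 0.95.

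Worst-case rounding moves each mean by 0.05 toward the other and adds 0.005 to each SD.

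| Contrast | d (mm) | s₁+s₂ | Printed p | p at r=−1 | p at r=0 | p at r=0.5 | Maximum with rounding |
|---|---|---|---|---|---|---|---|
| Table 1, baseline–3 | 0.4 | 0.94 | **0.9** | 0.211 | 0.092 | 0.028 | 0.344 |
| Table 1, baseline–6 | 1.3 | 1.09 | 0.001 | 0.004 | 0.0005 | <0.0001 | 0.007 |
| Table 1, 3–6 | 0.9 | 0.97 | 0.01 | 0.017 | 0.003 | 0.0003 | 0.030 |
| Table 2, baseline–3 | 0.1 | 1.07 | 0.1 | 0.774 | 0.695 | 0.601 | 1.0 |
| Table 2, baseline–6 | 0.6 | 1.22 | 0.2 | 0.154 | 0.056 | 0.013 | 0.231 |
| Table 2, 3–6 | 0.5 | 0.95 | **0.5** | 0.130 | 0.045 | 0.011 | 0.220 |

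The two bold cells are out of reach. The other four are attainable, though Table 2's 0.2 needs a clearly negative r. Table 2's 0.1 needs favourable rounding and r of about 0.74 or more: on the printed values the smallest p, at r = +1, is 0.27 (t = 0.1 × 3.162 / (0.67 − 0.40) = 1.17), and with rounding it is 0.04.

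**Unadjusted follow-up with pooled ANOVA error (df 18).** The variance of a difference can be at most the sum of the three squared SDs.

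- Table 1: 0.53² + 0.41² + 0.56² = 0.763; t = 0.4 × 3.162 / 0.873 = 1.45; p ≤ 0.165 (0.296 with rounding).
- Table 2: 0.67² + 0.40² + 0.55² = 0.911; t = 0.5 × 3.162 / 0.955 = 1.66; p ≤ 0.115 (0.206 with rounding).

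Neither reaches 0.9 or 0.5. A pooled error must also rank p-values by size of change, which Table 2 does not.

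**Bonferroni ×3 on the paired tests.** On printed values the maxima are 3 × 0.211 = 0.63 and 3 × 0.130 = 0.39. With rounding near its limits, a numerical search over valid correlation matrices does find fits to all three p-values in each table. They require a baseline to 3-month correlation of −0.52 or lower in the mVIP-CT arm and 0.955 or higher in the XCM arm, even when each printed p may be either rounded or truncated.

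**Where significance would change.** On printed values, the unadjusted p falls below 0.05 once r exceeds 0.31 (Table 1, baseline–3), 0.07 (Table 2, baseline–6) and −0.06 (Table 2, 3–6).

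**Secondary check, Table 9 at 6 months** ("6 months 1.207±0.16 0.97±0.31 0.06"). t = 0.237 / √((0.16² + 0.31²)/10) = 2.148. Student (df 18) gives p = 0.046, at most 0.054 with rounding. Welch (df 13.5) gives 0.050, at most 0.059. Welch can round to the printed 0.06, so no error is shown, but the variant is not stated and the result sits on the 0.05 line.

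**The case against.** The strongest reply is that the paired t sentence was meant for the two-visit bone data (Tables 7 and 8), and that the three-visit KTT cells come from an ANOVA follow-up or, after the Shapiro-Wilk screen, from a rank test. Data sets of 10 pairs can be built that match the printed means and SDs and give Wilcoxon p-values of 0.96 for the Table 1 cell and 0.44 to 0.51 for the Table 2 cell. Those need skewed differences, and all three cells of a table were not fitted jointly. So the documents cannot separate an arithmetic error from an unreported method. That stands. But on this reading the tables use a procedure the SAP never names, which is also a defect with the same remedy.

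Clerical slips are plausible too. In Table 1, 0.09 for 0.9 would fit r near 0. In Table 2, 0.05 for 0.5 would fit r near −0.06, or the first and third p-values may be swapped. The 0.09 reading and the swap would leave every contrast non-significant, so a change of significance is possible, not established. Either slip would still need correcting, and a swap in Table 2 does not explain Table 1.

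The odd ordering in Table 2 is not by itself an error under paired tests, because each pair of visits has its own correlation.

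The consequence is also limited. Section 3.1.1 makes no within-group significance claim that depends on these cells; its between-group statement, "at 3 and 6 month the differences were statistically significant", reproduces; and the mVIP-CT 6-month gain stays significant at any r.

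**Conclusion.** The concern holds. No within-patient correlation, with or without rounding, lets a two-sided paired t-test on 10 pairs give 0.9 in Table 1 (maximum 0.34) or 0.5 in Table 2 (maximum 0.22). The SAP states no other pairwise method that would. This rests on the printed means and SDs, n = 10 at each visit and two-sided testing; Table 3 supports the baseline, 3-month and 6-month KTT inputs.

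By contrast, all six within-group p-values for keratinized tissue width (Tables 4 and 5) are attainable with a paired t-test once rounding is allowed, so the problem is confined to KTT.

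This should be fixed, but it does not overturn the reported findings. The between-group KTT conclusions and Table 1's two significant contrasts stand. What is open is whether three contrasts shown as non-significant are so, and only patient-level data can settle that.

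**What to change.** - Re-run all six within-group KTT contrasts in Tables 1 and 2 from the patient-level data.
- State in the Statistical Analysis section which test produced the pairwise p-values in the three-visit tables (paired t, or a named follow-up to the repeated-measures ANOVA) and which adjustment, if any, was applied.
- Replace the printed values with exact p-values to three decimals, and give the mean change with its 95% CI for each contrast.
- As a secondary item, state which independent t-test variant gives the 6-month p-value in Table 9, and print the exact p with the matching interval. On printed values the difference is 0.237 mm, with 95% CI 0.005 to 0.469 (Student) or −0.0005 to 0.474 (Welch). Change section 3.2.1 only if the re-run requires it.

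The cost is six contrasts on existing data, one added methods sentence and two corrected tables. If XCM contrasts turn out significant, the within-group difference between the grafts will look less sharp.

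### The 6-month buccal cortex p-value of 0.06 (SAP Table 9) is not reproduced at the printed figures by either form of the independent t test, and the unstated form decides which side of 0.05 the result falls on.

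*SAP*

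**What the plan says.** The SAP's Statistical Analysis section gives the between-group method in one sentence: "Independent t test was used to compare means between two groups". It names the software ("Statistical analysis was performed with IBM® SPSS® (ver. 26") and the threshold ("A statistically significant level was considered when p value < 0.05"). It does not say whether equal variances were assumed, whether a variance test guided the choice, or whether tests were two-sided. The protocol's statistical section names no method.

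Table 9 gives the 6-month comparison under the column heads "mVIP-CTG (n= 10) Mean±SD" and "XCM (n=10) Mean±SD": 1.207±0.16 against 0.97±0.31, p = 0.06. The Results text says "there were no failed implants or withdrawal of any patients during the follow-up period", so 10 per arm should apply at 6 months too. Section 3.2.1 concludes "no significant differences between the study groups at baseline and follow up period".

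**The concern.** A two-sample t test can be rebuilt from two means, two SDs and two sample sizes, and Table 9 prints all six. The rebuilt p-value should match the printed one within rounding. Here it does not match directly, and the gap lies on the SAP's own decision threshold.

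The spread at 6 months is also quite different in the two arms (0.16 and 0.31). With equal arm sizes, both forms of the test give the same t statistic, but they refer it to different degrees of freedom. When the p-value is this close to 0.05, that difference is enough to move the result across the line.

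What is at stake is one stated between-group conclusion. Buccal bone thickness is the last of four assessments listed in the protocol, and no primary outcome is named, so the consequence is limited to that conclusion.

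**Working it through.** **Inputs.** From Table 9 at 6 months: mVIP-CT mean 1.207, SD 0.16, n = 10; XCM mean 0.97, SD 0.31, n = 10. Two-sided testing is assumed.

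**Check of the method on the baseline row.** For 0.744±0.33 against 0.92±0.32, both forms give p = 0.24. Table 9 prints 0.2, so that row agrees.

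**6-month row.**
- Difference = 1.207 − 0.97 = 0.237 mm.
- SE = √[(0.16² + 0.31²)/10] = √(0.1217/10) = 0.1103.
- t = 0.237/0.1103 = 2.148 under both forms.
- Student: df = 18, p = 0.0455. 95% CI = 0.237 ± 2.101 × 0.1103 = 0.005 to 0.469 mm.
- Welch: df = (v₁ + v₂)²/[(v₁² + v₂²)/9], with v₁ = 0.16²/10 = 0.00256 and v₂ = 0.31²/10 = 0.00961, so df = 13.5 and p = 0.0504. 95% CI = 0.237 ± 2.153 × 0.1103 = −0.0005 to 0.474 mm.

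Neither form gives 0.06.

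**Rounding.** The printed values allow means of 1.2065–1.2075 and 0.965–0.975, and SDs of 0.155–0.165 and 0.305–0.315. The largest p arises at 1.2065, 0.165, 0.975 and 0.315: t = 0.2315/0.11245 = 2.059. The smallest arises at the opposite corner: t = 0.2425/0.10819 = 2.241.

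| Form | p at printed values | p over rounding | Can print as 0.06? |
|---|---|---|---|
| Student | 0.046 | 0.038–0.054 | No |
| Welch | 0.050 | 0.043–0.059 | Only near the upper edge |

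Table 8's mean difference of −0.054 narrows the XCM mean to 0.9685–0.975. This raises the lower limits to 0.040 and 0.045 and leaves the upper limits unchanged.

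**Spread.** SD ratio = 0.31/0.16 = 1.94. Variance ratio = 3.75, F-test p = 0.06.

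**Baseline.** mVIP-CT started lower by 0.92 − 0.744 = 0.176 mm. Tables 7 and 8 give changes of +0.463 and +0.054 mm, which differ by 0.409 mm. The 6-month comparison in Table 9 takes no account of this.

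**Consistency of Table 7.** A paired p of 0.01 with 9 df corresponds to t = 3.250. SD of change = 0.463 × √10/3.250 = 0.451. The implied baseline-to-6-month correlation is (0.33² + 0.16² − 0.451²)/(2 × 0.33 × 0.16) = (0.1345 − 0.2030)/0.1056 ≈ −0.65. A strong negative correlation between two measurements of the same site is unusual, so this p-value should be checked as well.

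**The case against.** The strongest reply is that the printed 0.06 may be a correct Welch result. The SAP says only that an independent t test was used, and Welch's test is one. An SD ratio of 1.94 makes it a reasonable choice, and within rounding it reaches 0.059, which prints as 0.06. If the unrounded values are assumed uniform over their rounding intervals, about 7% of the possibilities give this, or about 11% when Table 8 is used to narrow the XCM mean. If the summaries were truncated rather than rounded, which is a further assumption, Student could reach 0.063 and Welch 0.068. This reply stands: an error in the cell is not proven.

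A reader might infer that the SAP's stated test contradicts its conclusion and that the bone result is really significant. The documents do not support that. They never name the Student form, Welch at the printed values is just above 0.05, and the Student range itself crosses 0.05.

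A reader might also back-calculate SDs of change from the paired p-values in Tables 7 and 8 and obtain a small p-value for the difference in change. That should not be used as support. It depends on p-values printed to one significant figure and on the implied correlation of about −0.65 in the mVIP-CT arm.

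Finally, the SAP specifies an unadjusted comparison, and the baseline difference was not significant. Lack of adjustment is therefore not an arithmetic error, and moving to an adjusted model after seeing a borderline result would be data-driven. That is a fair reason to label such a model as added and not to let it replace the stated test.

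**Conclusion.** The point holds in a limited form. At the printed figures the 6-month p-value is 0.046 (Student) or 0.050 (Welch), not 0.06. Student cannot print as 0.06 under ordinary rounding; Welch can, but only near the edge. Whether the 0.237 mm difference meets the p < 0.05 rule depends on a choice the SAP does not state, so the section 3.2.1 statement on follow-up cannot be verified from the summaries. They do not show the opposite either.

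This rests on 10 patients per arm at 6 months, two-sided tests, and means and SDs that were rounded in the usual way.

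**What to change.** 1. Recompute the 6-month comparison from patient data. State which form of the t test was used, and give p to three decimals with the difference and its 95% CI.
2. Add, labelled as an added analysis, an ANCOVA of 6-month thickness adjusted for baseline thickness, with a 95% CI. Report it beside the recomputed test.
3. Check the paired p of 0.01 in Table 7 against the patient data.
4. Correct the Table 9 cell and the section 3.2.1 sentence to match the recomputed result. If the interval only just includes or excludes zero, say so and do not rely on the significance label alone.

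The cost is small: the measurements are already held, and the work is one re-run comparison, one added model, one check, one table cell and one sentence.
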